### **7.5.1.2 Classifications for adverse event assessment**

All AEs will be assessed and documented by the investigator according to the categories detailed below.

#### **7.5.1.2.1 Seriousness**

For each AE, the seriousness must be determined according to the criteria given in Section 7.5.1.1.

#### **7.5.1.2.2 Intensity**

In this follow-up study, the intensity of an AE is classified according to the NCI-CTCAE grading (Version 4.03) as defined in each of the feeder trials.

#### **7.5.1.2.3 Causal relationship**

*Section modified by Amendment 2 (Section 13.2.1.2 and 13.2.1.9).*

Only radium-223 dichloride-/placebo-related AEs and related SAEs will be collected and recorded in this study. All occurrences of leukemia, myelodysplastic syndrome, aplastic anemia, and primary bone cancer or any other new primary malignancy must be reported as SAEs at any time, and regardless of the investigator's causality assessment. All bone fractures and bone associated events (e.g., osteoporosis) should be collected as either AEs or SAEs if the criteria of SAE were met, regardless of the investigator's causality assessment.

The assessment of the causal relationship between an AE and the radium-223 dichloride/placebo treatment is a decision to be made by the investigator, who is a qualified physician, based on all information available at the time of the completion of the eCRF.

The assessment is based on the question whether there was a “reasonable causal relationship” to radium-223 dichloride/placebo.

Possible answers are “yes” or “no”

An assessment of “no” would include:

1. The existence of a highly likely alternative explanation, e.g., mechanical bleeding at surgical site.

or

2. Non-plausibility, e.g., the subject is struck by an automobile when there is no indication that the drug caused disorientation that may have caused the event; cancer developing a few days after the first drug administration.

An assessment of “yes” indicates that the AE is reasonably associated with the use of radium-223 dichloride/placebo.

Important factors to be considered in assessing the relationship of the AE to radium-223 dichloride/placebo include:

- The temporal sequence from drug administration during the feeder trial:  
The event should occur after the drug was given. The length of time from drug exposure to event should be evaluated in the clinical context of the event.
- Underlying, concomitant, intercurrent diseases:  
Each event should be evaluated in the context of the natural history and course of the disease being treated and any other disease the subject may have.
- Concomitant medication or treatment:  
The other drugs the subject is taking or the treatment the subject receives should be examined to determine whether any of them might have caused the event in question.
- Known response pattern for this class of drug: clinical / preclinical
- Exposure to physical and / or mental stresses:  
The exposure to stress might induce adverse changes in the recipient and provide a logical and better explanation for the event.
- The pharmacology and pharmacokinetics of the study treatment:  
The pharmacokinetic properties (absorption, distribution, metabolism and excretion) of radium-223 dichloride/placebo, coupled with the individual subject's pharmacodynamics should be considered.
- The assessment is not possible

#### **7.5.1.2.4 Action taken with study treatment**

Not applicable to this follow-up study.

#### **7.5.1.2.5 Other specific treatment(s) of adverse events**

- None
- Remedial drug therapy

- Other

### 7.5.1.2.6     Outcome

The outcome of the AE is to be documented as follows:

- Recovered / resolved
- Recovering / resolving
- Recovered / resolved with sequelae
- Not recovered / not resolved
- Fatal
- Unknown

### 7.5.1.3     Assessments and documentation of adverse events

*Section modified by Amendments 1 (Section 13.1) and 2 (Section 13.2.1.2).*

The investigator has to record on the respective eCRF pages all radium-223 dichloride-/placebo-related AEs ongoing at or occurring from the time of the signing of the ICF and the end of the study. The type of information that should be assessed and recorded by the investigator for each AE is listed in Section 7.5.1.2.

Each event should be described in detail along with start and stop dates (onset and resolution of event), intensity, temporal and causal relationship to feeder trial-related investigational product and / or protocol-related procedures, possible alternative factors (co-morbidities, co-medications), therapeutic action taken, result of therapeutic action, and ultimate outcome of the AE. The investigator's assessment of AEs with grades and causality assessments must be documented and retained in the source documentation.

If more than one radium 223-dichloride- or placebo-related AE occurs, each event should be recorded separately. All AEs and SAEs are to be followed until resolved or as clinically required.

All occurrences of leukemia, myelodysplastic syndrome, aplastic anemia, and primary bone cancer or any other new primary malignancy must be reported as SAEs at any time, and regardless of the investigator's causality assessment. All bone fractures and bone associated events (e.g., osteoporosis) should be collected as either AEs or SAEs if the criteria of SAE were met, regardless of the investigator's causality assessment. If a subject is unable to provide required details for events of interest, this information will need to be obtained from the primary provider.

Adverse events may be reported spontaneously by the subject, the subject's health care professional, or the subject's caregiver, or elicited through questioning during each follow-up telephone call and / or visit during the study. Subject data collected at other standard-of-care visits and / or contacts may be used to satisfy study-required data. As far as possible, all radium-223 dichloride-/placebo-related AEs must be described by their duration (start and stop date), severity (graded according to the NCI-CTCAE, Version 4.03), relationship to treatment, and according to the need of other specific therapy. All information will be recorded in the source documentation and AE eCRF.

“Death” should not be recorded as an AE on the AE page. Instead, “death” is the outcome of underlying AE(s).

For all SAEs the sponsor has to carry out a separate assessment for expectedness, seriousness and causal relationship to radium-223 dichloride/placebo.

#### **7.5.1.4 Reporting of serious adverse events**

*Section modified by Amendment 2 (Section 13.2.1.2).*

The definition of SAEs is given in Section 7.5.1.1. Each SAE must be followed up until resolution or stabilization by submission of updated reports to the designated recipient.

If disease progression leads to signs and symptoms that meet the criteria for seriousness (e.g., hospitalization), the associated signs and symptoms should be reported as SAEs, not the underlying cause (i.e., “progressive disease” should not be recorded as an SAE). In this case, disease progression should be mentioned on the SAE form as an “alternative explanation.”

#### **Reporting of additional malignancies**

All occurrences of leukemia, myelodysplastic syndrome, aplastic anemia, and primary bone cancer or any other new primary malignancy must be reported as SAEs at any time, regardless of the investigator's causality assessment.

#### **Reporting of bone fractures and bone associated events**

All bone fractures and bone associated events (e.g., osteoporosis) should be collected as SAEs if the criteria of SAE were met, regardless of the investigator's causality assessment.

#### **Investigator's notification of the sponsor**

All investigators will be thoroughly instructed and trained on all relevant aspects of the investigator's reporting obligations for SAEs. This information, including all relevant contact details, is summarized in the Investigator Site File. This information will be updated as needed.

The investigator must report immediately (within 24 hours of the investigator's awareness) all SAEs considered to be related to radium-223 dichloride/placebo; all occurrences of leukemia, myelodysplastic syndrome, aplastic anemia, and primary bone cancer or any other new primary malignancy; and bone fractures and bone associated events (e.g., osteoporosis; (if the criteria of SAE were met, regardless of the investigator's causality assessment) occurring during the observation period defined in Section 7.5.1.3 to the recipient detailed in the instructions for SAE reporting included in the Investigator File. For this, an AE page in the eCRF as well as the complementary pages provided in the Investigator File must be completed for each SAE.

Any SAEs occurring after the protocol-defined observation period will be processed by the sponsor according to all applicable regulations.

Any CTCAE Grade 4 screening laboratory abnormality that is part of the disease profile should not be reported as an SAE, specifically when they are allowed or not excluded by the

protocol inclusion / exclusion criteria. If an investigator is in doubt about the applicable reporting obligations, he / she should consult with the study monitor for the sponsor.

### **Notification of the Independent Ethics Committees / Institutional Review Boards**

Notification of the Independent Ethics Committees (IECs) / Institutional Review Boards (IRBs) about all relevant events (e.g., SAEs, suspected, unexpected, serious adverse reactions [SUSARs]) will be performed by the sponsor and / or by the investigator according to all applicable regulations.

### **Notification of the authorities**

The processing and reporting of all relevant events (e.g., SAEs, SUSARs) to the authorities will be done by the sponsor according to all applicable regulations.

### **Sponsor's notification of the investigational site**

The sponsor will inform all investigational sites about reported relevant events (e.g., SUSARs) according to all applicable regulations.

#### **7.5.1.5      Expected adverse events**

For this study, the applicable reference document is the most current version of the IB / summary of product characteristics.

Overview listings of frequent events that have occurred so far in the clinical development are shown in the current IB. If relevant new safety information is identified, the information will be integrated into an update of the IB and distributed to all participating sites.

The expectedness of AEs will be determined by the sponsor according to the applicable reference document and according to all local regulations.

#### **7.5.2      Pregnancies**

The investigator must report to the sponsor any pregnancy occurring in a female study subject during her participation in this study. The outcome of the pregnancy should be followed up carefully, and any outcome of the mother and the child at delivery should be reported.

For a pregnancy in the partner of a male study subject, all efforts will be made to obtain information on course and outcome, subject to the partner's consent.

For all reports, the forms provided are to be used. The investigator should submit them within the same timelines as an SAE.

#### **7.6      Other procedures and variables**

Not applicable to this follow-up study.

#### **7.7      Appropriateness of procedures / measurements**

The procedures chosen for the evaluation of long-term safety in this study population are consistent with the appropriate ethical standards used in studies of oncology drugs.

## 8. Statistical methods and determination of sample size

### 8.1 General considerations

Statistical analysis will be performed using Statistical Analysis Software; the version used will be specified in the statistical analysis plan (SAP).

### 8.2 Analysis sets

*Section modified by Amendment 1 (Section 13.1).*

**Safety:** All subjects who have received at least 1 dose of radium-223 dichloride or placebo in the feeder trials. This safety population will be used in the analysis of all safety endpoints. Subjects will be included in the analyses according to the treatment they received.

### 8.3 Variables and planned statistical analyses

#### 8.3.1 Primary and secondary variables

The primary and secondary variables are as defined in Section 3.2.

#### 8.3.2 Statistical and analytical plans

*Section modified by Amendment 1 (Section 13.1).*

Studies of all clinical phases with different designs and different endpoints will be included in the evaluation. There will be separate analyses of the individual feeder trials, and pooled analysis of the final data across studies, as appropriate.

All statistical analyses will be descriptive in nature. In general, summary statistics (n, mean, standard deviation, median, minimum, maximum, and 95% confidence intervals for continuous variables, and number of subjects and percentage in each category for categorical variables) will be provided.

No formal statistical testing is planned for the overall analysis. Source data for summaries will be presented as subject data listings.

The details for analyses will be specified in the SAP.

#### 8.3.2.1 Safety analysis

*Section modified by Amendments 1 (Section 13.1) and 2 (Section 13.2.1.2).*

Adverse events will be coded using the standard Medical Dictionary for Regulatory Activities and grouped by system organ class and preferred term. Events will be summarized by frequency and proportion of total subjects, system organ class, and preferred term.

The safety data from feeder trials and 16996 will be combined within each study for all AE summaries. For pooled analyses, all data across the selected feeder trials and 16996 will be combined by treatment groups and by treatment doses, as appropriate. Separate summaries will be given for: all events related to study drug, all events by NCI-CTCAE grade, SAEs, and AEs leading to death.

Deaths and SAEs will be summarized and listed.

The incidence of leukemia, myelodysplastic syndrome, aplastic anemia, and primary bone cancer or any other new primary malignancy; the incidence of bone fractures and bone associated events (e.g., osteoporosis); and for subjects who receive cytotoxic chemotherapy, the incidence of febrile neutropenia or hemorrhage during their chemotherapy treatment and for up to 6 months thereafter, will be summarized using statistical measures that will depend upon whether the study includes a comparator group or is a single-cohort study. Other considerations include the length of follow-up time and time-to-event methods.

Statistical measures that can be used include incidence proportion, incidence rate, and cumulative incidence (or competing risk approach). Definitions of each measure will be described in detail in the SAP.

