### **Definition of serious adverse event**

An SAE is classified as any untoward medical occurrence that, at any dose, meets any of the following criteria (a - g):

- a. Results in death
- b. Is life-threatening

The term ‘life-threatening’ in the definition refers to an event in which the subject was at risk of death at the time of the event, it does not refer to an event which hypothetically might have caused death if it were more severe.

- c. Requires inpatient hospitalization or prolongation of existing hospitalization

A hospitalization or prolongation of hospitalization will not be regarded as an SAE if at least one of the following exceptions is met:

- The admission results in a hospital stay of less than 12 hours
- The admission is pre-planned (e.g., elective or scheduled surgery arranged prior to the start of the study; admission is part of the study procedures as described in Section 7.2).
- The admission is not associated with an AE (e.g., social hospitalization for purposes of respite care)

However, it should be noted that invasive treatment during any hospitalization may fulfill the criterion of ‘medically important’ and as such may be reportable as an SAE dependent on clinical judgment. In addition, where local regulatory authorities specifically require a more stringent definition, the local regulation takes precedence.

- d. Results in persistent or significant disability / incapacity

Disability means a substantial disruption of a person's ability to conduct normal life's functions.

- e. Is a congenital anomaly / birth defect
- f. Is another serious or important medical event as judged by the investigator
- g. Is an occurrence of leukemia, myelodysplastic syndrome, aplastic anemia, and primary bone cancer or any other new primary malignancy (regardless of the investigator's causality assessment)

If disease progression leads to signs and symptoms that meet the criteria for seriousness (e.g., hospitalization), the associated signs and symptoms should be reported as SAEs, not the underlying cause (i.e., "progressive disease" should not be recorded as an SAE). In this case disease progression should be mentioned on the SAE form as an "alternative explanation."

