Per protocol, febrile neutropenia and hemorrhage AEs are to be collected during and within 6 months of cytotoxic chemotherapy treatment. For the protocol-specified analysis of the incidence of febrile neutropenia or hemorrhage during their chemotherapy treatment and for up to 6 months thereafter, a simplified analysis will be performed, of febrile neutropenia and hemorrhage AEs without regard to cytotoxic chemotherapy association. All 16996-emergent febrile neutropenia and hemorrhage AEs documented in the study CRF will be reported, without regard to chemotherapy treatment.

For the analysis of fractures and bone associated events, separate analyses of patients with bone fractures, patients with bone associated events, and patients with bone fractures and/or bone associated events will be performed. The applicable MedDRA appendix will identify the MedDRA preferred terms applicable to each sub-category.

Unless otherwise specified, the analysis for each AE category will include a summary of the total number and percent of SAF-LTF participants with an AE of the applicable category. Participants with an applicable AE will be summarized by MedDRA preferred term (PT), overall within each applicable MedDRA system organ class (SOC), and overall (any applicable AE), both by worst CTCAE grade and for any grade. For summaries by worst grade, the AE with the worst grade in the applicable summary category will be used. AEs with missing grade will be included in any-grade summaries but not in summaries by worst grade. In addition, listings will be provided.

6.4.2.1 16996-Collected Adverse Events

All AEs collected in study 16996, whether or not collection was required per study 16996 protocol, will be listed for SAF-LTF including AE PT, 16996-emergent (Y/N), start and stop dates, grade, treatment-related (Y/N), serious (Y/N), reason for seriousness, outcome of AE, and time (days) since last dose of study drug. The listing will include all 16996-collected AEs, whether or not emerging within study 16996.

6.4.2.2 16996-Emergent Adverse Events

Summaries of the total number and percent of SAF-LTF participants with an AE of the following categories of 16996-emergent AEs will be presented:

• All 16996-emergent adverse events

Statistical Analysis Plan

Protocol No.: BAY 88-8223/16996

Page: 13 of 17

- Radium-223 dichloride- or placebo-related 16996-emergent AEs;
- Radium-223 dichloride- or placebo-related serious 16996-emergent AEs;

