- 16996-emergent new primary malignancies;
- 16996-emergent bone fractures;
- 16996-emergent serious bone fractures;
- 16996-emergent bone-associated events;
- 16996-emergent serious bone-associated events;
- 16996-emergent pregnancy AEs;
- 16996-emergent febrile neutropenia and hemorrhage without regard to cytotoxic chemotherapy status.

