7.2 Changes in Per-Protocol Planned Statistical Analyses

Per the Sponsor decision to perform a reduced and simplified analysis focusing on data from study 16996, the following deviations from the per-protocol planned analyses have been noted in this SAP:

- Section 4. Analysis Sets
 - o Addition of of ENR and SAF-LTF analysis sets
 - o Removal of SAF analysis set;
 - Accounting for the assignment of participants enrolled in 16996 from non-eligible feeder trials.
- Section 5. General Statistical Considerations
 - o Removal of safety data combination between feeder studies and study 16996;
 - Description of limited data integration (including baseline characteristics and exposure);
 - o Description of interim safety analyses to meet Health Authority requirements.
- Section 6. Statistical Methodology
 - Summary of all febrile neutropenia and hemorrhage events collected in study 16996 without regard to chemotherapy treatment;
 - o Definition of 16996-emergent AEs.

Protocol No.: **BAY 88-8223/16996** Page: 17 of 17

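### The SAP omits the protocol's overall SAE summary and its summary of AEs leading to death, and does not declare either omission in Section 7

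*Protocol*

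**What the plan says.** Protocol 8.3.2.1 (Safety analysis) sets the AE reporting: "Separate summaries will be given for: all events related to study drug, all events by NCI-CTCAE grade, SAEs, and AEs leading to death". It then adds: "Deaths and SAEs will be summarized and listed". The SAE definition in Protocol 7.5.1.1 includes, as criterion g and regardless of causality: "Is an occurrence of leukemia, myelodysplastic syndrome, aplastic anemia, and primary bone cancer or any other new primary malignancy".

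SAP 6.4.2.2 names ten categories to be tabulated on the SAF-LTF set. The first is "All 16996-emergent adverse events". Three are restricted to serious events: "Radium-223 dichloride- or placebo-related serious 16996-emergent AEs", "16996-emergent serious bone fractures" and "16996-emergent serious bone-associated events". The other six are related AEs, new primary malignancies, bone fractures, bone-associated events, pregnancy AEs, and febrile neutropenia with hemorrhage. SAP 6.4.2 gives each category by preferred term, by system organ class and overall, for any grade and by worst grade.

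SAP 6.4.2.1 lists all AEs collected in 16996, with seriousness, reason for seriousness and outcome. SAP 6.4.2.3 tabulates and lists deaths with the investigator's primary cause.

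SAP 7.2 is the place for departures from the protocol's analysis. It says "the following deviations from the per-protocol planned analyses have been noted in this SAP" and itemizes them by section.

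**The concern.** A study whose primary variables are all safety variables would normally report how many participants had any SAE and how many had an AE that ended in death. The protocol promises both. Under this SAP the only serious table that spans event types is limited to events the investigator judged related, and no table is defined by fatal outcome.

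A reader of the clinical study report who wants either number would have to build it from listings. A reader who checks SAP 7.2 for what changed would not learn that these two summaries had gone.

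**Working it through.** No arithmetic in the plan needs reproducing. The check sets each promised summary beside the SAP.

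**Step 1. Promised against planned.**

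| Protocol 8.3.2.1 | SAP |
|---|---|
| Events related to study drug | Kept (6.4.2.2) |
| Events by CTCAE grade | Kept (6.4.2, worst grade within each category) |
| SAEs, summary | No overall table; three partial serious rows |
| AEs leading to death, summary | None |
| Deaths, summary and listing | Both kept (6.4.2.3) |
| SAEs, listing | Kept, as a flag in the listing of all collected AEs (6.4.2.1) |

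Of the four separate summaries, 4 − 2 = 2 are missing.

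**Step 2. Is it declared?** The Section 6 items in SAP 7.2 are the febrile neutropenia and hemorrhage simplification and the definition of 16996-emergent AEs. SAP 7.1 records for version 2 that incidence rates and cumulative incidence rates were removed. Neither section mentions the SAE or fatal-AE summaries, so 0 of 2 omissions are declared.

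**Step 3. Can the missing SAE count be rebuilt from the tables?** Let A, B, C and D be the numbers of participants with related serious AEs, serious fractures, serious bone-associated events, and new primary malignancies. D belongs here because criterion g makes every such event an SAE. Let E be the number with any other SAE, that is, one judged unrelated and outside B to D. Then

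max(A, B, C, D) ≤ participants with any SAE ≤ A + B + C + D + E.

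- The groups overlap. One participant with a related serious fracture is counted in both A and B, so the sum counts one person twice.
- E is not tabulated. It includes unrelated serious febrile neutropenia and hemorrhage. The SAP summarizes that category, but without a serious subset, so the row only caps this part of E.

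The tables therefore bound the number but do not give it.

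**Step 4. Can the fatal-AE count be rebuilt?** The death table counts all deaths by primary cause. Protocol 7.5.1.3 treats death as the outcome of an underlying AE rather than as an AE, and Protocol 7.5.1.2.6 records outcome, including fatal, for each AE. A death with no collected AE behind it appears in the death table but would not be an AE leading to death. The two counts are different quantities.

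**The case against.** The strongest reply is that little is hidden. The study collects only related AEs and SAEs plus named categories. Related SAEs, which are the primary variable, are tabulated. New primary malignancies, including leukemia, myelodysplastic syndrome and aplastic anemia, have a table with no causality filter, and serious fractures and serious bone-associated events have their own rows. All of this stands.

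A reader might infer that the SAEs the study was set up to find drop out of the tables when judged unrelated. The documents do not support that. Such events can be absent from the related-serious row, but they are counted in their own category. For the same reason, the 12 new malignancies that Protocol 1.1 reports from the phase 3 trial do not measure a loss. Events of that kind would be in the malignancy table if 16996-emergent, and the protocol does not give the investigators' causality answers for them.

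A second reply is that fatal AEs would show in the worst-grade rows. That may be so if every fatal AE carries the top CTCAE grade. This is an assumption, because the documents do not reproduce the grade definitions and they record intensity and outcome as separate items. SAP 6.4.2 also leaves AEs with missing grade out of the worst-grade summaries. Grade gives no route at all to seriousness.

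A third reply is that the SAP announces a reduced analysis in general terms. It does, but Sections 1, 4.1, 5.1 and 7.2 describe that reduction as a focus on data from 16996 instead of combined feeder data. An SAE table built from 16996 data alone fits within it. The history entry for SAP version 1.1 records an option to replace tables with listings when few AEs are reported. The version 2 text carries no such option, and it was conditional in any case.

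Finally, the supplemental SAP for Health Authority Reports (SAP 5.5) and the sponsor's display standards (SAP 5.1) were not available, so they may include these tables. That would not correct the final-analysis SAP or its list of deviations.

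**Conclusion.** The point holds as a discrepancy between protocol and SAP: two of four promised summaries are absent and neither omission is declared. Three things follow:

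- No table gives the number of participants with any SAE.
- No table is defined by an AE of fatal outcome.
- Serious febrile neutropenia or hemorrhage judged unrelated is counted in no serious table.

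It would go too far to say that fatal events are uncounted, since deaths are tabulated with primary cause. The loss is in tabulation; nothing disappears from the listings.

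The size is the two summaries. The documents give no event counts from 16996 with which to put a number on the affected participants. The conclusion rests on SAP 6.4.2.2 being the complete list of AE tables for the final analysis.

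**What to change.** Add two tables to SAP 6.4.2.2, on SAF-LTF, by feeder study and treatment arm:

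- (a) participants with any serious 16996-emergent AE regardless of causality, by system organ class and preferred term, with an overall row;
- (b) participants with a 16996-emergent AE of fatal outcome, in the same layout.

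Footnote (a) to say that unrelated SAEs outside the named categories were not systematically collected, so the count is of SAEs collected and not of all SAEs that occurred. A separate serious row for febrile neutropenia and hemorrhage is optional: the protocol does not promise one, and table (a) would show these events.

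If the sponsor prefers to leave the tables out, SAP 7.2 should name both omissions and give the reason.

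The cost is two standard tables. Seriousness, reason for seriousness and outcome are already in the planned listing, so no new data are needed, and the change restores an analysis the protocol already contains.
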